### **6.0 Treatment Plan**

All patients will receive the class I, HLA-A2 restricted gp100(g209-2M) peptide vaccine. Patients who are HLA-DP4 positive will also receive the class II restricted MAGE-3 peptide, in separate extremities. This will allow us to generate melanoma-specific CD8+ and CD4+ T-cells. The gp100(g209-2M) immune response will be our primary endpoint for assessment of T-cell priming, since we have extensive previous experience with this vaccine and believe that CD8+ responses are critical to the development of a strong antitumor immune response. The MAGE-3 peptide will be given in order to stimulate antigen-specific CD4+ T-cells, which we believe are also important in the generation of strong antitumor immunity. Patients positive for both HLA types will

receive both vaccines, gp100(g209-2M) and MAGE-3, for eight weeks. Patients who are HLA-A2 positive and HLA-DP4 negative will receive only the gp100 peptide for 8 weeks. There will be two arms in Part 1: Arm A is the peptide vaccines plus the TLR7/8 agonist, R848 and Arm B is the peptide vaccines only. All patients will be randomized to either Arm A or Arm B by CORe during the registration process. The randomization will be stratified by cohort (metastatic disease or adjuvant). In Arm A, R848 gel will be applied to the gp100(g209-2M) vaccine injection site immediately following the injection. The R848 gel will be allowed to air dry for 30 minutes and then covered with a gauze dressing. All vaccines will be administered subcutaneously and intradermally. The gp100(g209-2M) peptide will be administered in the same extremity weekly (every 7 days +/- 2 days) for 8 weeks. Similarly, in a separate extremity of eligible patients, the MAGE-3 peptide will be administered weekly (every 7 days +/- 2 days) for 8 weeks. Each syringe (a total of 4, 2 for gp100 and 2 for MAGE-3) will contain 1ml of peptide vaccine; 0.5ml of the vaccine in each syringe will be administered intradermally and the other 0.5ml will be administered subcutaneously at each injection site for a total of 4 sites.

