## 11.0 Statistical Considerations

### Overview

This is a randomized phase II trial enrolling melanoma patients who are HLA-A2+ with or without HLA-DP4+. Patients of two separate types will be enrolled in separate cohorts. One cohort includes patients who are NED but at high risk for recurrence. The second cohort will include patients with non-visceral metastatic disease and must have at least two evaluable and biopsiable lesions to be eligible for the trial.

The trial will have two parts. In Part 1 (both cohorts), we will fairly randomize patients to receive either the gp100(g209-2M) +/-MAGE3 peptide vaccine plus a topical TLR 7 /8 agonist, R848, (Arm A) or the gp100(g209-2M) +/- MAGE3 vaccine alone Arm B). The randomization will be stratified by cohort. A total of 48 patients will be enrolled, 24 per arm. All patients will receive the gp100(g209-2M) vaccine (those who are HLA-DP4 + will also receive the MAGE3 vaccine) weekly (for 8 weeks) and the patients randomized to receive R848 gel will have the gel applied to the gp100(g209-2M) vaccine site weekly.

After 8 weeks of treatment on Part 1, Part 2 of the trial begins. In Part 2 (only patients in the metastatic disease cohort), the treating physician will divide the area of cutaneous lesions into regions, Region A and Region B and designate the two regions to receive or not to receive R848. At least one lesion will be randomly assigned to receive R848 from weeks 8 through 24, and one will not. One lesion from each region will be chosen for biopsy as outlined in section 7.3. If a patient has more than two evaluable lesions, we will stratify by lesion size to assure that the lesions will be comparable.

As a safety measure, if a patient's untreated lesions grow while treated lesions are stable or shrink, all lesions will be treated with R848. This will occur after the assessment of the primary endpoints of the study, so it will not affect the analysis of these endpoints.

In April 2015, the trial is being further modified to add an additional 20 patients with metastatic disease, all of whom will receive the the gp100(g209-2M) +/-MAGE3 peptide vaccine plus R848 (Arm C). These patients will not be part of the primary comparative study analysis of T-cell responses in the blood. The purpose of these patients is to provide additional information on characterizing tumor response, defined as at least a 50% shrinkage in tumor size by irRC criteria.

### Part 1

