The primary objective of Part 1 of the trial is to compare T-cell responses in the blood between the vaccine+R848 and vaccine alone treatment arms. This will be assessed in the two cohorts separately and combined. The primary outcome of this part of the trial will be T-cell response to gp100(g209-2M) +/- MAGE3 measured at 8 weeks using a tetramer/multimer assay measured by flow cytometry. Based on the number of gp100(g209-2M) +/- MAGE3 T-cells measured, when the study began, patients were to be categorized as either immune responders or immune non-responders. From previous vaccine studies, a  $\geq 0.1\%$  response was thought to be a reasonable target. Thus, T-cell response to the gp100(g209-2M) + / - MAGE3 peptide in each patient was

defined as  $\geq 0.1\%$  gp100(g209-2M) tetramer+ cells in the CD8+ T-cell population or  $\geq 0.1\%$  MAGE3 multimer cells in the CD4+ T-cell population. In September 2013, due to problems in obtaining the multimers necessary to perform the CD4+ T-cell assays, these assays have not yet been run, although more than 24 patients have reached week 24 on the trial. Based upon the aggregate CD8+ responses, no patients have met the definition of response according to the above definition. Therefore, the study team is changing the definition of the primary endpoint to be the actual change from baseline for gp100(g209-2M) tetramer+ cells in the CD8+ T-cell population. The study will be stratified by cohort (NED/metastatic), but we expect the same immune response in each cohort.

For part 1 the 8-week primary immune outcome values CD8+ T-cell response will be compared between the two arms by using a Wilcoxon rank-sum test. Patients who discontinue from the study before week 8 will be assigned the lowest rank in this analysis. With one interim analysis, using an O'Brien-Fleming boundary to stop for efficacy, a one-sided significance level of 0.05, with 24 patients per arm, we will have 80% power to be able to detect an effect size of  $0.73^*SD(CD8+ T\text{-cell response})$ .

## Part 2

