A sample size argument for Part 2, based upon a 2-sample t-test (which represents a lower bound on the mixed-effects model given above), is as follows: we assume that a total of 24 patients will be enrolled in the metastatic disease cohort, and of these, 17% of the patients initially enrolled will discontinue the trial at 8 weeks due to progressive disease and that dropout will be equally distributed across the 2 arms, leaving a total of 20 patients (10/arm) for Part 2. The 2-sample t-test will assess differences in the change between the two treatment groups with respect to the 3 outcomes described previously. With 20 patients, we will have 80% power to detect an increase of 1.2 standard deviations in the R848 group for each outcome at 8 weeks, assuming a one-sided 2-sample t-test with a 5% Type I error rate. One of the benefits of our mixed-effects modeling approach is that it allows for the analysis of the data using complete likelihood methods (Beunckens, Molenberghs, and Kenward, 2005; Clinical Trials). In addition, we will perform 2 types of sensitivity analysis: 1) We will use last-observation-carried-forward; 2) We will explore how deviations from the Missing at Random (MAR)

assumption of the direct likelihood approach may impact inference using methods developed in Verbeke and Molenberghs (2000).

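### The plan does not say whether the Part 1 primary Wilcoxon test is stratified by cohort; an unstratified test gives up power if the cohorts differ in overall response level

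*Combined protocol and SAP*

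**What the plan says.** Section 6.0 and the Section 11.0 Overview both stratify the Part 1 randomisation by cohort. The Overview puts it as "The randomization will be stratified by cohort. A total of 48 patients will be enrolled, 24 per arm". Section 11.0, Part 1 then adds: "The study will be stratified by cohort (NED/metastatic), but we expect the same immune response in each cohort".

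The primary test is described once, in Part 1: the 8-week values "will be compared between the two arms by using a Wilcoxon rank-sum test". Early discontinuation is handled by ranking: "Patients who discontinue from the study before week 8 will be assigned the lowest rank in this analysis". On the population, the primary objective carries the sentence "This will be assessed in the two cohorts separately and combined". The power statement (80% for 0.73 SD, one-sided 0.05, one O'Brien-Fleming interim) is for 24 patients per arm. No section names a stratified rank test.

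**The concern.** The sentence that the study is stratified could refer to the randomisation, the analysis or both. Two statisticians could run different primary tests and each claim to follow the plan. The lowest-rank rule is open in the same way: lowest overall, or lowest within cohort.

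The choice affects efficiency. Stratified randomisation balances the cohorts across the arms, so a level difference between cohorts contributes almost nothing to the true variability of the arm comparison. The ordinary rank-sum variance still counts that spread as noise. The test is then conservative and loses power. Ranking within cohort removes the spread.

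The plan also does not say whether the separate or the combined result decides the primary objective. The 24-per-arm power statement implies the combined one.

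**Working it through.** **Inputs.** 48 patients, 24 per arm (Section 11.0, Overview). Effect 0.73 SD, one-sided 0.05 (Part 1). Nominal levels 0.0056 at the interim and 0.0482 at the final look (Study Stopping Criteria). For the cohort split, Part 2 says "we assume that a total of 24 patients will be enrolled in the metastatic disease cohort", which leaves 48 − 24 = 24 adjuvant patients; this is taken as 12 per arm in each cohort. The cohort level difference is assumed at 0 to 1.5 SD, because the documents give none.

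**The plan's own figure.** Power ≈ Φ(0.73 × √(24/2) − z). At one-sided 0.05 this is Φ(2.529 − 1.645) = 81.2%; at 0.0482 it is 80.7%. The two-look calculation gives 80.9%, or 79.3% after the Wilcoxon efficiency factor 3/π. The two nominal levels together give an overall one-sided error of 0.04997. The stated 80% is reproduced.

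**The two tests.** The unstratified test ranks all 48 patients together. The van Elteren test ranks within cohort *s* and sums (W_s − n_s(N_s + 1)/2)/(N_s + 1) over cohorts, divided by its standard error, where W_s is the Arm A rank sum, n_s the Arm A number and N_s the cohort size.

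**Simulation.** 100,000 trials per scenario, both tests on the same data, normal outcomes with SD 1 within cohort, interim at 6 per arm per cohort, tie-corrected normal approximation. *Unstrat.* means unstratified at both looks. *Strat.* means unstratified at the interim and van Elteren at the final look. Van Elteren at both looks is within 0.2 points of *Strat.* throughout. Reading (a) takes 0.73 in within-cohort SD. Reading (b) takes it in overall SD, so the effect is 0.73 × √(1 + shift²/4) = 0.730, 0.752, 0.816 and 0.912.

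| Cohort shift (SD) | Power (a) Unstrat. | Power (a) Strat. | Power (b) Unstrat. | Power (b) Strat. | One-sided error Unstrat. | One-sided error Strat. |
|---|---|---|---|---|---|---|
| 0 | 78.1% | 77.6% | 78.3% | 77.5% | 5.1% | 5.2% |
| 0.5 | 76.2% | 77.4% | 78.6% | 79.7% | 4.5% | 5.0% |
| 1.0 | 70.9% | 77.3% | 79.7% | 84.7% | 3.3% | 5.0% |
| 1.5 | 61.5% | 77.4% | 81.3% | 91.1% | 1.8% | 4.8% |

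An uneven split of 8 metastatic and 16 adjuvant per arm (final look only, 40,000 trials) gives a similar pattern: 71.9 v 77.2% at 1 SD.

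**Where stratifying costs power (Unstrat. v Strat.).**
- Equal cohorts: 78.11 − 77.63 = 0.48 points under (a).
- R848 effect of 0.73 ± 0.25, 0.5 or 0.73 SD by cohort, same vaccine-alone level: 77.2 v 76.5%, 74.2 v 73.3%, 69.7 v 68.6%.
- One or two metastatic discontinuations per arm before week 8 (assumed), lowest rank, no shift: 72.2 v 71.4%, 66.4 v 66.3%.
- Least favourable case tried, with vaccine-alone levels offset so that overall cohort means are equal despite the differing R848 effects: 77.6 v 76.5%, 76.1 v 73.5%, 74.5 v 68.9%.

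**Which result decides.** Within one cohort (12 per arm, 0.0482, factor 3/π), power is Φ(0.73 × √(12 × 0.955/2) − 1.663) = 53%. Only the combined comparison is powered.

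**The case against.** The strongest case is that nothing is wrong. The named test is valid, its error is never above the planned level beyond simulation noise, and the stated power reproduces. The plan expects equal response in the cohorts, and on that expectation the stratified test is slightly worse. At a 0.25 SD difference the two are practically equal (77.5 v 77.3%, final look only). The endpoint is a change from baseline, so cohort differences in pre-vaccine level are already subtracted. The larger losses need assumed shifts of 1 SD or more. The plan expresses its effect in SDs of the CD8+ response without mentioning cohort, which favours reading (b), and there power never falls below 78.3%. Early dropout for progression in the metastatic cohort, one cohort difference the plan does foresee, gives no reason to stratify on its own. Finally, this would be a second change to the primary analysis after aggregate CD8+ responses were seen.

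All of this is accurate, and it limits the point to an optional improvement. It does not remove the ambiguity. The expectation of equal cohorts has no supporting data in the documents, and the cohorts differ clinically: disease-free against measurable metastatic disease. If a stratified test was always intended, one sentence settles the matter.

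**Conclusion.** The point holds as an efficiency matter. The plan leaves open whether its primary test is stratified. If it is not, and the cohorts differ in overall level, power under reading (a) is lower than it need be by 77.4 − 76.2 = 1.2 points at 0.5 SD, 77.3 − 70.9 = 6.4 at 1 SD and 77.4 − 61.5 = 15.9 at 1.5 SD. Under reading (b) the plan keeps its power and forgoes a gain of 1.1, 5.0 and 9.8 points. With no level difference nothing is lost. Stratifying does not help if only the R848 effect differs between cohorts.

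These sizes rest on assumed cohort shifts, normal outcomes and an even cohort split. The direction (conservative, never anti-conservative) does not depend on the size of the shift.

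**What to change.** Add to Section 11.0, Part 1:

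> At the final analysis the primary test is a one-sided van Elteren (cohort-stratified Wilcoxon) test on all 48 randomised patients at nominal 0.0482. Patients who discontinue before week 8 take the lowest rank within their own cohort. This combined test alone decides the primary objective; the separate cohort results are descriptive, and the unstratified rank-sum test is a sensitivity analysis.

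Leave the interim as it was run, and use the stratified test there only if the interim has not yet been done. Its trigger (24 of 48 patients at week 8) had evidently been passed by September 2013, when the plan's endpoint change was justified "although more than 24 patients have reached week 24 on the trial". The documents do not say whether the look took place.

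Record, with a date, that the test was chosen before anyone choosing it saw results by arm, or disclose that it was not. If the team prefers the unstratified test, say so explicitly and make van Elteren the sensitivity analysis; that is the less disruptive option and also removes the ambiguity.

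The cost is a few sentences and the dated record, with no new patients or data. In power, the stratified choice costs about 0.1 to 1.1 points if the cohorts share the same vaccine-alone level, and about 1 to 6 points in the least favourable case tried.

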## 2.12 MAGE-3 peptide vaccines

MAGE family antigens are also attractive targets for the development of cancer vaccines, because they are tumor specific, and are shared by different types of cancers. Among these, MAGE-3 is the most frequently expressed in melanomas, with 55% expression in melanoma primary lesions, and 74% in metastatic lesions. Several MAGE-3 peptides were identified that can be recognized by CD4 $^{+}$  T cells that are restricted by MHC class II molecules. Specifically, MAGE-3243-258 peptide (KKLLTQHFVQENYLEY) was identified to be presented by HLA-DP4 molecules, a HLA class II allele expressed by approximately 76% of Caucasians. Exposure of MAGE-3243-258 peptide presented by DP4 molecules to specific CD4 $^{+}$  T cell clones resulted in a robust production of IFN- $\gamma$ . Furthermore, this specific CD4 $^{+}$  T cell clone exhibited lytic activity against melanoma cells mediated by the recognition of MAGE-3243-258 antigen. MAGE-3 antigens have been used in several small-scale therapeutic trials. The vaccines consisted of an antigenic peptide, a protein, a pox family recombinant

virus carrying a MAGE-3 sequence, or dendritic cells (DCs)-pulsed with an antigenic peptide. No significant toxicity was observed. Clinical responses were observed in a small number of patients.

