## Study Stopping Criteria

We will conduct an interim analysis after half of the patients have been enrolled and have reached week 8 on the study. At the interim analysis, we will test whether there is strong evidence that the immune responses differ between the two treatment arms. We will use an O'Brien-Fleming stopping boundary to stop for efficacy, with a nominal significance level of 0.0056. With the alpha spent at the interim look, the nominal significance level at the final analysis will be 0.0482.

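### HLA-DP4 status decides who also receives MAGE-3 but is neither a randomisation stratum nor a term in the Part 1 primary test: a precision and chance-imbalance point, not a validity fault

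*Combined protocol and SAP*

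**What the plan says.** Section 11.0, Overview: "All patients will receive the gp100(g209-2M) vaccine (those who are HLA-DP4 + will also receive the MAGE3 vaccine". The same section states "A total of 48 patients will be enrolled, 24 per arm". Sections 6.0 and 11.0 stratify the randomisation by cohort (metastatic or adjuvant) and by nothing else.

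Section 6.0 explains that MAGE-3 is given to stimulate CD4+ T-cells, "which we believe are also important in the generation of strong antitumor immunity". It is injected in a separate extremity, and R848 goes on the gp100 site only.

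Under Part 1, the current primary endpoint is the change from baseline in gp100 tetramer-positive CD8+ cells, which "will be compared between the two arms by using a Wilcoxon rank-sum test". Patients who discontinue before week 8 take the lowest rank. The comparison is to be made in each cohort and combined. Neither DP4 status nor cohort appears as a term in the test, and no analysis by DP4 status is described. HLA-DP4 typing is a pretreatment test (Section 5.8).

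**The concern.** DP4 type is the one recorded baseline factor that changes the regimen, yet the plan makes no use of it. Cohort, by contrast, is a stratum although Part 1 expects the same immune response in both cohorts.

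If receiving MAGE-3, or DP4 type itself, shifts the gp100 CD8+ response, two things follow. Variation between regimens stays in the error term when it could be removed. And a chance difference between arms in the DP4-positive share would look like an R848 effect, or mask one. If such an imbalance showed up in a 48-patient trial with nothing prespecified, the only remedy would be a post hoc adjustment, which readers may discount.

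**Working it through.** **Inputs.** From the plan: 24 per arm; "a one-sided significance level of 0.05"; "we will have 80% power to be able to detect an effect size of" 0.73 times the SD of the CD8+ response; one interim look "with a nominal significance level of 0.0056" and 0.0482 at the end. DP4 prevalence p = 0.76, from Section 2.12 ("a HLA class II allele expressed by approximately 76% of Caucasians"), is assumed to hold for the trial population. The DP4 effect h, in within-regimen SD, is not given in the documents, so a range is shown.

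**1. The plan's own power.** Normal approximation: 0.73 × √(24/2) = 2.529, and Φ(2.529 − 1.645) = 81.2%. With the Wilcoxon efficiency 3/π: 2.529 × √0.955 = 2.471, and Φ(0.826) = 79.6%. At 0.0482 the two figures are 80.7% and 79.1%; with both looks, 80.9% and 79.3%. The stated 80% is reproduced, and so are the two nominal levels.

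**2. Does omitting DP4 lower that power?** Total SD = √(1 + p(1−p)h²), with p(1−p) = 0.76 × 0.24 = 0.1824. This is 1.023 at h = 0.5 and 1.087 at h = 1. The plan's 0.73 multiplies the total SD, so any DP4 variation is already inside it. Simulated unadjusted power stays at about 77–78% for every h from 0 to 1.5.

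**3. What adjustment could add.** With the DP4 variance removed, the standardised effect becomes 0.73 × 1.023 = 0.746 (h = 0.5) or 0.73 × 1.087 = 0.794 (h = 1). Formula power at one-sided 0.05 with the Wilcoxon efficiency rises from 79.6% to about 81% and 85%. The formula ignores the cost of estimating the DP4 term. Simulation of the rank-sum test against rank regression gives gains of under 1 point at h = 0.5 and about 5 points (4 to 5 across runs) at h = 1. At h = 0 the two differ by no more than about 1 point.

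**4. How often chance imbalance arises.** The SD of the between-arm difference in DP4-positive share is √(2 × 0.1824/24) = 0.123, or 12 points. From two independent binomials (24, 0.76), a gap of at least 4 patients has probability 23.5%. A gap of at least 6 has probability 6.2%, or 3.1% in each direction. At the interim, with 12 per arm, the SD is √(2 × 0.1824/12) = 0.174.

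**5. What a gap of 6 does when R848 has no effect.** With 21 of 24 DP4-positive in one arm and 15 of 24 in the other, the arm difference shifts by 0.25h. The within-arm variance is 1 + h² × (0.109 + 0.234)/2 = 1 + 0.172h². The true standard error, given the DP4 counts, is √(2/24) = 0.2887. The rejection probability is 1 − Φ(1.645 × √(1 + 0.172h²) ∓ 0.25h/0.2887).

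| DP4-positive, R848 arm vs vaccine-alone arm | h | Normal formula | Simulated rank-sum |
|---|---|---|---|
| 21 vs 15 | 0.5 | 10.6% | 10% |
| 21 vs 15 | 1 | 18.0% | 17% |
| 15 vs 21 | 0.5 | 1.7% | 2% |
| 15 vs 21 | 1 | 0.4% | 0.4% |

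The DP4-adjusted rank analysis stays near 5% in all four settings. Averaged over all randomisations, the unadjusted test also rejects in about 5% of trials.

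**The case against.** The case for leaving the test alone has real force.

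- **No DP4 effect is documented.** Section 6.0 says that CD4+ cells matter for antitumor immunity in general; it does not say that MAGE-3 raises circulating gp100-specific CD8+ cells. Section 3.3 places priming in the regional lymph nodes and puts the two peptides in separate extremities, which argues against cross-help at priming. This stands, so every gain above is conditional.
- **Validity is intact.** Both arms follow the same DP4-dependent rule, and randomisation controls the error rate. This also stands.
- **A second late change has a cost.** The primary endpoint was already redefined after more than 24 patients had reached week 24, and the interim was due once half had reached week 8. The documents do not say whether by-arm results have been seen. This stands, and it governs how the change should be made.

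A reader might infer that power falls well below 80%. That follows only if 0.73 is read as a within-regimen SD (about 72% at h = 1), and Part 1 does not define it that way. A reader might also take 10% or 17% as the trial's false-positive rate. Those figures apply to one imbalance in one direction; a gap that large in that direction has probability 3.1%, and the mirror case is conservative.

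What the objection does not remove is that DP4 type is already recorded, alters treatment, and costs almost nothing to adjust for.

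**Conclusion.** The omission is real, and its consequence is modest and conditional. The 80% power and the roughly 5% overall one-sided error both hold, so this is not bias and not an underpowered design. If DP4 status shifts the gp100 response, adjustment gains under 1 point of power at 0.5 within-regimen SD and about 5 points at 1 SD. It also keeps the conditional error near 5% when the arms happen to differ in DP4 share. If there is no shift, little is gained or lost.

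These figures assume 76% DP4-positive, normally distributed outcomes, no early discontinuation and a single look at one-sided 0.05. At a prevalence of 50–60%, a gap of at least 4 patients would occur in 30–31% of trials.

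**What to change.** Before any unblinded by-arm analysis, specify the Part 1 primary comparison as a rank-based ANCOVA: regress the overall ranks on arm, HLA-DP4 status and cohort as main effects, and keep the lowest-rank rule for early discontinuation. Cohort belongs in the model because it is the randomisation stratum. Main effects are preferable to full cross-stratification: at 76% prevalence only about 6 DP4-negative patients per arm are expected (0.24 × 24 = 5.8), and a van Elteren test stratified by DP4 costs 1–2 points if DP4 is irrelevant. Report DP4 balance by arm.

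If by-arm data have already been seen at the interim, keep the Wilcoxon test as primary and report the DP4- and cohort-adjusted rank analysis as a labelled sensitivity analysis.

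The cost is SAP wording and one or two degrees of freedom, with at most about a point of power if DP4 does not matter. No new data are needed.

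### The Part 1 power of 80% at 0.73 SD states no distribution and no allowance for the plan's own lowest-rank rule; under normal data it holds only with essentially no discontinuation before week 8

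*Combined protocol and SAP*

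**What the plan says.** Section 11.0, Overview, sets the size of the randomized comparison: "A total of 48 patients will be enrolled, 24 per arm". Under Part 1 the endpoint is the change from baseline in gp100 tetramer-positive cells within the CD8+ population. The 8-week values "will be compared between the two arms by using a Wilcoxon rank-sum test". The next sentence sets the rule for early losses: "Patients who discontinue from the study before week 8 will be assigned the lowest rank in this analysis". The power statement follows directly. It assumes one O'Brien-Fleming interim look for efficacy and a one-sided 0.05 level, and it claims that "with 24 patients per arm, we will have 80% power to be able to detect an effect size of" 0.73 SD.

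Study Stopping Criteria gives the timing, "We will conduct an interim analysis after half of the patients have been enrolled and have reached week 8 on the study", and nominal levels of 0.0056 at the interim and 0.0482 at the final analysis.

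The documents do not say which formula produced the 80%, which distribution the SD-based effect refers to, or how many patients are expected to discontinue before week 8.

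**The concern.** The analysis rule and the power claim stand next to each other, yet the claim shows no sign of the rule. When discontinuations occur in both arms, the patients tied at the bottom carry no information about the treatment effect but stay in the ranking, so they dilute a true difference. Losing as few as 2 of 48 patients in this way could matter.

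At stake is how the primary result is read. At 80% power, a true 0.73 SD effect is missed 20% of the time. At 67% power it is missed 33% of the time. A null result judged against the stated figure would then be taken as stronger evidence against R848 than the design can give.

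**Working it through.** **Inputs from the documents.** n = 24 per arm; effect δ = 0.73 SD; one-sided α = 0.05; interim at half the patients, so 12 per arm; nominal levels 0.0056 and 0.0482; Wilcoxon rank-sum test; lowest rank for discontinuation before week 8.

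**Assumptions of mine.** Normal data with a pure location shift; equal numbers lost per arm, from 0 to 3; lost patients tied at the lowest rank.

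**1. Reproduce the stated figure.** For a two-sample t-test the noncentrality is δ√(n/2) = 0.73 × √12 = 2.529 on 2n − 2 = 46 degrees of freedom.
- At level 0.05 the critical value is 1.679 and power is 80.1%. The effect giving exactly 80% is 0.729 SD.
- At the final level 0.0482 the critical value is 1.697 and power is 79.6%.
- With both looks, by simulation, power is 79.9%.

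A two-sided 0.05 test would give about 70%, so the one-sided reading is the right one.

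**2. Check the interim.** With Lan-DeMets O'Brien-Fleming spending at half the information, the interim level is 2[1 − Φ(1.96/√0.5)] = 2[1 − Φ(2.772)] = 0.0056. The matching final level is 0.0482, and total α is 0.0500. The levels are correct, and the look costs only about 0.3 to 0.5 points of power.

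**3. Large-sample allowance for the rank test.** Multiplying n by the normal-data efficiency 3/π gives a drift of 0.73 × √(12 × 3/π) = 2.471. Two-look power is then 79.3%, which also rounds to about 80%.

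**4. The planned test at the planned size.** I simulated the rank-sum test with both looks, δ = 0.73 SD. The normal-data entries cover repeated runs of 40,000 to 200,000 trials:

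| Lowest-rank patients per arm | Normal data | t(5) data |
|---|---|---|
| 0 | 77.8-78.2% | 86% |
| 1 | 72-73% | 81% |
| 2 | 66-67% | 76% |
| 3 | 58-59% | 69% |

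With exact p-values and no losses, normal data give 77.2-77.5%. The change of test therefore costs about 2 to 3 points, and each of the first two losses per arm costs about 6 more.

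Equal counts are not the pessimistic choice. With losses occurring at random at 8.3% (2 of 24), power is 64%. At 2%, 5% and 10% it is 75%, 70% and 61%.

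**5. Effect detectable with 80% power, normal data.** About 0.76 SD with no losses (80.3% by the exact test), 0.81 SD with one per arm, 0.86 SD with two and 0.94 SD with three.

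**6. Other distributions.** With 0, 1, 2 and 3 lost per arm:
- logistic: 82%, 77%, 71%, 64%
- Laplace: about 89%, 85%, 80%, 73%
- exponential: 94%, 92%, 89%, 84%

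The starting level changes, but power falls with each loss in every case.

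**The case against.** Three objections have force.

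**Origin of the figure.** A reader might infer that the 80% was computed with a t-test and is therefore an arithmetic error. The documents do not support that, because no formula is named. The rank-test approximation in step 3 gives 79.3%, which a planner could fairly quote as 80%. The match to a t-test calculation is a fact, but its use is not established. Without discontinuations the gap is 2 to 3 points, which is small for a planning figure.

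**Distribution.** A reader might infer that the design falls short of 80% whatever the data look like. That is not supported either. The endpoint is a change in a cell percentage and the plan chose a rank test, so skewed or heavy-tailed data are plausible. With no losses, every non-normal shape tried gives more than 80%, and with exponential data power stays above 80% at three losses per arm. Normality is the usual reading of an effect stated in SD units, but it remains an assumption.

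**Discontinuation rate.** A reader might apply the 17% drop-off in Sections 6.0 and 11.0 and conclude that power is about 49%. That figure is drop-off at week 8 in the metastatic cohort and is used to size Part 2; it is not a pre-week-8 rate for Part 1. Section 10.1 also lets patients whose disease progresses in the first 10 weeks stay on study, and lets either cohort complete laboratory evaluations after recurrence or progression before week 16. That removes part of the main cause of early loss.

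What remains is that Sections 10.2 to 10.5 still allow loss before week 8 through withdrawal of consent, adverse events, physician decision or missed visits. The plan writes a rule for such patients, and its power statement shows no allowance for that rule.

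**Conclusion.** The point holds as a gap in the power statement. The stated 80% at 0.73 SD agrees with a t-test calculation with no discontinuations. Under normal data and equal losses, the planned two-look rank-sum test has about 77-78% power with none lost, 72% with one per arm, 67% with two and 58% with three. The lowest-rank rule accounts for most of the shortfall; the choice of test adds little and the interim almost nothing.

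The size rests on a distribution and a discontinuation count that the documents do not supply. With t(5) data, power drops below 80% only at two losses per arm; with strongly skewed data it need not drop below 80% at all. The direct conclusion is that a reader cannot tell under what conditions the 80% applies, and under the usual normal reading it does not survive even one discontinuation per arm.

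**What to change.** Replace the power sentence in Section 11.0, Part 1, with one computed for the planned rank-sum test, including the interim look and the lowest-rank rule. It should name the assumed distribution and a range of pre-week-8 discontinuations. For example: *Assuming normally distributed changes and equal losses per arm, the two-look Wilcoxon test with 24 patients per arm has 80% power at about 0.76 SD with no discontinuation before week 8, 0.81 SD with one per arm and 0.86 SD with two per arm.* If the sponsor's assay data suggest a skewed or heavy-tailed distribution, give the same figures for that shape.

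The cost is one sentence. Enrolment, test, boundaries and the lowest-rank rule stay as they are. The only downside is a slightly less favourable stated figure.
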